## 6 Research question and objectives

The purpose of the Siponimod Pregnancy Exposure Registry is to evaluate the effect of siponimod exposure on rates of pregnancy and infant outcomes in exposed pregnancies compared to unexposed disease-matched and healthy unexposed pregnancies. The lack of human fetal safety data for siponimod makes such a monitoring system an important component of epidemiologic research on the safety of this drug.

The primary objective is to estimate and compare the prevalence of major structural defects in siponimod exposed pregnant women versus 1) disease-matched pregnant women not exposed to siponimod, and 2) healthy pregnant women.

The primary objective will be evaluated among i) pregnancies ending in at least one live birth, and ii) pregnancies ending in at least one live birth, spontaneous abortion, still birth or termination of pregnancy

Secondary objectives are to estimate and compare the prevalence of selected adverse pregnancy and infant outcomes in siponimod-exposed pregnant women versus 1) disease-matched pregnant women not exposed to siponimod, and 2) healthy pregnant women.

Mayzent exposure is defined as exposure to siponimod any time from the 4th days post the first day of LMP prior to conception up to and including the end of pregnancy.

- The primary outcome of the study is major structural defects.
- The secondary outcomes of the study are:
  - Spontaneous abortion/miscarriage
  - Stillbirth
  - Elective termination
  - Preterm delivery
  - Preeclampsia / eclampsia
  - Pattern of 3 or more minor structural defects
  - Small for gestational age
  - Postnatal growth small for age at approximately one year of age
  - Developmental performance at approximately one year of age
  - Serious or opportunistic infections in the first year of life.

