Elective termination / abortion	Outcome – secondary	Maternal report Medical record	A deliberate discontinuation of pregnancy through medication or surgical procedures.
Premature delivery	Outcome - secondary	Maternal report Medical record	A spontaneous or induced delivery at <37.0 gestational weeks (as counted from LMP), reported by the mother and validated through the medical record.
Preeclampsia / Eclampsia	Outcome - secondary	Maternal report Medical record	Reported by maternal interview and confirmed with medical records.
Small for gestational age	Outcome - secondary	Maternal report Medical record	Birth size (weight, length or head circumference) $\leq 10^{\text{th}}$ percentile for sex and gestational age using National Center for Health Statistics (CDC, 2000) pediatric growth curves for full term infants. Prenatal growth curves specific to preterm infants will be used for premature infants (Olsen, 2010).
Postnatal growth deficiency	Outcome - secondary	Medical record	Postnatal size (weight, length or head circumference) $\leq 10^{\text{th}}$ percentile for sex and age using NCHS pediatric growth curves (CDC, 2000), and adjusted postnatal age for premature infants.
Screening for Developmental Milestones	Outcome - secondary	Neurodevelopmental questionnaires	Screening for neurodevelopment performed using the Ages and Stages Questionnaire (ASQ). An abnormal score is defined in the scoring guidelines.
Serious or Opportunistic Infections	Outcome - secondary	Maternal report Medical record	Defined as tuberculosis, x-ray proven pneumonia, neonatal sepsis, meningitis, bacteremia, invasive fungal infection, pneumocystitis, septic arthritis, osteomyelitis,

Variable	Role	Data source(s)	Operational Definition
			abcess (deep tissue), and infections requiring hospitalization, identified in live born infants up to one year of age.
Maternal Age (years)	Confounder	Maternal report	Maternal age (years) at due date, continuous and categorical (<25, 25-29, 30-34, >34).
Paternal Age (years)	Confounder	Maternal report	Paternal age (years) at due date, continuous and categorical (<25, 25-29, 30-34, >34).
Maternal Race	Confounder	Maternal report	Maternal (Caucasian/White, Black, Asian/Pacific Islander, Native American, Other).
Maternal Ethnicity	Confounder	Maternal report	Maternal (Hispanic, Non-Hispanic).
Maternal Education	Confounder	Maternal report	Maternal Educational Category (years of completed education <12, 12-15, >15).

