### 7.5.1 Determination of sample size

The sample size for this study is not only based on the statistical considerations to address the question of interest but also takes into account the feasibility aspects, prior experience and available literature ([Krueger et al 2017](#)) on conduct of pregnancy registries in the MS disease area.

In the three cohorts, approximately 867 pregnant women will be enrolled in US and Canada with a ratio of 1:1:1.

Based on previous experience with MotherToBaby/OTIS Pregnancy Studies, it is estimated that subjects will be an average of 7-10 weeks post-LMP at the time of enrollment. Given this mean gestational timing at enrollment, the anticipated spontaneous abortion/stillbirth rate is 10%, the estimated elective abortion rate is 5%, and the estimated lost to follow-up rate is 5% ([Chambers et al, 2016](#)). This will result in known outcomes for approximately 273 pregnancies in each cohort, including 231 pregnancies with at least one live born infant in each cohort at the end of recruitment.

Baseline rates of major structural birth defects, specific patterns of three or more minor structural defects, premature delivery, and small for gestational age are based on previous MotherToBaby/ OTIS studies and on general population data. Rates of spontaneous abortion in the general population are 15-20% ([Avalos AL, et al 2012](#), and [Magnus et al 2019](#)). However, since women do not typically enroll in pregnancy registries until after 7-8 weeks' gestation when the highest risk of spontaneous abortion has passed, the baseline estimate is drawn from previous OTIS studies. [Table 7-4](#) gives the minimum detectable effect sizes with 80% power (two-sided significance level 0.05, except as noted below for pattern of minor structural defects), for the comparisons described above. If the disease-matched comparison and the healthy comparison groups are comparable, then consideration will be given to pooling data in the two comparisons cohorts for analysis, as shown in [Table 7-5](#). The current sample size provides 80% power to detect a risk ratio of approximately 4.4 or greater in major structural defects compared to the baseline prevalence of 3% in the comparison groups. This is consistent with the population prevalence of major structural defects of 2.8% in the Atlanta metropolitan area ([CDC 2017](#)).

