#### **7.7.2.4 Outcome classification for secondary outcomes**

- ***Spontaneous abortion:*** spontaneous abortion/miscarriage is defined as non-deliberate fetal death which occurs prior to less than 20.0 weeks post-LMP.
- ***Analysis subset:*** the analysis subset for the secondary outcome of spontaneous abortion will be restricted in Cohort 1 to those who were exposed to any dose from

the 4th day post first day of LMP prior to conception to 20 weeks' gestation and enrolled prior to 20 weeks' gestation. The analysis subset for cohorts 2 and 3 will be restricted to those who enrolled prior to 20 weeks' gestation.

- **Stillbirth:** stillbirth is defined as non-deliberate fetal death anytime in gestation at or after 20 weeks post-LMP.
- **Elective termination:** elective termination/abortion is defined as deliberate termination of pregnancy at any time in gestation. Reasons for elective abortions are captured and are classified as due to medical reasons or social reasons.
- **Premature delivery:** premature delivery is defined as live birth prior to 37.0 weeks gestation as counted from LMP (or calculated from first-trimester ultrasound-derived due date if last menstrual period uncertain or more than 1 week discrepant). Elective caesarian deliveries or inductions prior to 37.0 completed weeks will be considered separately.
- **Preeclampsia / eclampsia:** preeclampsia or eclampsia reported by maternal interview with confirmation in medical record or report by medical record only is captured.
- **Small for gestational age:** small for gestational age is defined as birth size (weight, length or head circumference) less than or equal to the 10th centile for sex and gestational age using standard pediatric CDC growth curves for full term or preterm infants (CDC, 2000; Olsen et al., 2010).
- **Minor structural defects:** a minor structural defect is defined as a defect which has neither cosmetic nor functional significance to the child (e.g., complete 2,3 syndactyly of the toes). Minor structural defects will be identified only through the study dysmorphology examination for live born infants using the study-specific checklist.

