#### 7.7.3.1.1 Analyses of the primary outcome

The primary outcome of interest, i.e. major structural defects, will be estimated in each cohort as a proportion (95% CI) using two denominators i) pregnancies ending in at least one live born infant and ii) pregnancies ending in at least one live born infant, stillborn, spontaneous abortion or elective termination. Data will also be presented by gestational timing of exposure.

For the primary endpoint, the exposure of interest is siponimod exposure at any time from the 4th day post the first day of the LMP prior to conception to the end of the first trimester, whether or not there is continued exposure to siponimod in the second or third trimesters. The primary comparison will be the rate of major structural defects between the siponimod-exposed group and comparison group 1 (disease-matched comparison group) among pregnancies resulting in at least one live born infant. A point estimate of the crude (i.e. unadjusted) risk ratio (RR) of the siponimod-exposed group versus comparison group 1, as well as its 95% confidence interval (CI) will be computed.

The same analysis will be repeated using the second numerator and denominator encompassing pregnancies ending in at least one live births, stillbirth, spontaneous abortion or elective termination, but excluding those lost-to-follow-up.

Due to the observational nature of the study, the above crude estimate of RR will be further adjusted for potential confounders (Rosenbaum, 2002), provided that there are sufficient numbers of events. A complete list of potential confounders, which includes but not limited to the baseline characteristics, will be provided in the SAP for each outcome prior to the final analysis, based on scientific knowledge including literature review.

As a primary approach, following Levenson and Yue, 2013, all potential confounders will be accounted for in the propensity score model.

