### **7.7.3.1.2 Analyses of secondary outcomes**

The analysis of spontaneous abortion (SAB) and stillbirth: Only those subjects who are enrolled prior to 20 weeks of gestation are eligible for the analysis of SAB. Since they are not followed from gestational age zero, survival analysis methods will be used to handle left truncation, as well as right-censoring when a subject is lost-to-follow-up prior to 20 weeks' gestation. Left-truncated Kaplan-Meier estimate at 20 weeks' gestation will be used to estimate the SAB rate in each of the cohorts (Tsai et al, 1987). The Cox proportional hazards regression models incorporating left truncation will be used to estimate the hazard ratio (HR) of different cohorts, as well as to obtain the 95% CIs. Stillbirth will be analyzed in a similar fashion. To account for potential confounding, PS methods described above will be applied, where regression adjustment will be used with the Cox model to obtain the adjusted HR.

The analysis of premature delivery: Only those subjects who are enrolled prior to 37 weeks of gestation are eligible for the analysis of premature delivery. These data will be analyzed similarly to SAB, as described above, using survival analysis methods to handle possible right-censoring.

The following will be considered binary endpoints: preeclampsia/eclampsia, small for gestational age (SGA) at birth in weight, height and head circumference, respectively, and growth deficiency at about one year of age in weight, height and head circumference respectively. The analysis of each of these outcomes will be similar to the analysis of the primary outcome, based on all pregnancies resulting in live born infants excluding twins or higher order multiples.

Multiple births will be included in the analyses of minor structural defects, ASQ, and serious or opportunistic infections. These outcome variables will thus likely contain correlated data due to twins or higher order multiples, and the generalized estimating equations (GEE) approach will be used (Liang and Zeger, 1986, Diggle et al, 2002).

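### Preeclampsia/eclampsia has two conflicting case definitions and is analysed only in singleton live-birth pregnancies; the first must be reconciled, the second is a small but unexplained restriction

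*Protocol*

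**What the plan says.** **Case definition.** The operational definition in Table 7-1 is "Reported by maternal interview and confirmed with medical records". Section 7.7.2.4, which classifies the secondary outcomes, says "preeclampsia or eclampsia reported by maternal interview with confirmation in medical record or report by medical record only is captured".

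**Analysis set.** Section 7.7.3.1.2 begins its list with "The following will be considered binary endpoints: preeclampsia/eclampsia, small for gestational age (SGA) at birth in weight, height and head circumference", adds growth deficiency at about one year, and says that each is analysed like the primary outcome, "based on all pregnancies resulting in live born infants excluding twins or higher order multiples".

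**Objective.** Section 6 sets the secondary objective as estimating and comparing the "prevalence of selected adverse pregnancy and infant outcomes in siponimod-exposed pregnant women" with the two comparison groups. It names no live-birth or singleton limit.

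**Related rules.** Stillbirth is a separate secondary outcome: "stillbirth is defined as non-deliberate fetal death anytime in gestation at or after 20 weeks post-LMP". A wider analysis that brings in losses is given for the primary outcome only (Section 7.7.3.1.1): "The same analysis will be repeated using the second numerator and denominator encompassing pregnancies ending in at least one live births, stillbirth", and so on through the other losses.

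**The concern.** There are two separate problems.

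**The definitions give different case counts.** A woman whose chart documents preeclampsia but who did not mention it at interview is a case under Section 7.7.2.4 and a non-case under Table 7-1. This is a realistic situation. As Section 7.4.3 describes the interviews, none after enrollment names preeclampsia:
- Intake asks about current complications, but enrollment averages 7-10 weeks (Section 7.5.1).
- The interim calls update exposures, prenatal tests and contact details.
- The live-birth outcome interview asks about delivery or birth complications.
- The interviews for losses list no maternal complications.

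The actual forms may ask more, but on this description the record is a main route to case finding. The objective is to estimate prevalence as well as compare it, so an undercount matters even when it is equal across cohorts.

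**A maternal outcome is conditioned on live birth.** Size at birth and growth at one year need a live infant; preeclampsia does not. A woman with preeclampsia and a stillbirth leaves both numerator and denominator. Stillbirth occurs after exposure and is itself an outcome that exposure might affect, so the restriction selects on something downstream of exposure. If late loss with preeclampsia were commoner in the exposed cohort, the observed risk ratio would be too low.

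**Working it through.** **1. The plan's own counts.** Section 7.5.1 says "approximately 867 pregnant women will be enrolled in US and Canada with a ratio of 1:1:1", that is 867 / 3 = 289 per cohort. It anticipates 10% spontaneous abortion or stillbirth, 5% elective abortion and 5% lost to follow-up.
- Known outcome: 289 x 0.95 = 274.6 (stated: 273).
- Live birth: 289 x (1 - 0.10 - 0.05 - 0.05) = 231.2 (stated: 231).

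Both reproduce closely. The difference is 273 - 231 = 42 pregnancies per cohort, or 15% of those with known outcome. Most of these are spontaneous abortions and terminations (289 x 0.10 = 28.9 spontaneous abortions and stillbirths together; 289 x 0.05 = 14.5 elective). The stillbirth share is not given.

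**2. What the protocol does not give.** There is no preeclampsia rate, no row for it in Table 7-4 or 7-5, no stillbirth rate separate from spontaneous abortion, and no share of multiples. Everything below rests on assumed inputs.

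**3. Cases per cohort**, risk x 231:

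| Assumed risk | Cases |
|---|---|
| 3% | 6.9 |
| 5% | 11.6 |
| 8% | 18.5 |

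**4. Loss under the Table 7-1 rule**, cases x share found only in the record, with an assumed share of 5-30%:
- At 5% risk: 11.6 x 0.05 = 0.6; 11.6 x 0.20 = 2.3; 11.6 x 0.30 = 3.5.
- Over the whole range: 6.9 x 0.05 = 0.3 up to 18.5 x 0.30 = 5.5.

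**5. Loss under the live-birth rule**, late losses x share of them with preeclampsia. Assume about 245 continuing pregnancies, 0.5-1% fetal death after 20 weeks, and preeclampsia in 5-25% of those deaths:
- Late losses: 245 x 0.005 = 1.2 to 245 x 0.01 = 2.5.
- Cases lost: 1.2 x 0.05 = 0.06 to 2.5 x 0.25 = 0.6 per cohort.

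**6. Effect on the risk ratio.** Let f be the share of preeclampsia cases ending in fetal death. Ignoring the small change in denominators, observed RR = true RR x (1 - f exposed) / (1 - f comparator). With a true RR of 2.0 and 2% in the comparator:

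| f exposed | Observed RR |
|---|---|
| 5% | 2 x 0.95 / 0.98 = 1.94 |
| 10% | 2 x 0.90 / 0.98 = 1.84 |
| 20% | 2 x 0.80 / 0.98 = 1.63 |

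The last row is extreme. With 2 x 11.6 = 23.1 exposed cases, 20% is 4.6 fetal deaths with preeclampsia, more than the 1.2-2.5 late losses of every cause assumed in step 5. If instead the 0.6 cases of step 5 (0.6 / 11.6, about 5%) were lost from the exposed cohort alone, a true RR of 2.0 would read about 2 x 0.95 = 1.9.

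**7. Sampling error for comparison.** With 12 v 12 cases in 231 per group, the SE of log RR is sqrt(2/12 - 2/231) = 0.40, so the 95% CI is about 0.46 to 2.18.

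**The case against.** **On the definitions.** Section 7.7.2.4 is the classification section and the more specific text, and it accepts record-only cases outright. Table 7-1 is a general list that names both data sources, and Section 7.3 leaves further detail to the SAP. An analyst following Section 7.7.2.4 loses nothing. This limits the consequence: record-only cases drop out only if Table 7-1 prevails. It does not remove the conflict, because both rules are fixed in the protocol and any SAP must depart from one of them.

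**On the denominator.** Sections 7.7.2.3 and 7.9 explain the live-birth set for the primary outcome by uneven prenatal diagnosis and pathology and by unknown malformation status in losses. That reason concerns birth defects and carries little weight for a maternal diagnosis. It is also fair that stillbirth is analysed separately and that each exposed stillbirth is reported to the sponsor within 24 hours (Section 9.2.1), so these pregnancies stay visible; only their preeclampsia status leaves the comparison.

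**Stronger readings to avoid.** A reader might infer the following:
- That the 42 excluded pregnancies per cohort measure the loss. They are mostly spontaneous abortions and terminations.
- That the animal data in Section 5 predict the bias. They report post-implantation loss, embryo-fetal deaths and abortions without singling out late loss, and early losses would not remove preeclampsia cases.
- That the cases removed are always the most severe. The protocol does not grade severity.

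**Conclusion.** Both points stand, with different weight. The conflict between Table 7-1 and Section 7.7.2.4 is firm and needs no assumption. If the stricter rule were applied, prevalence would be understated and perhaps 1 to 4 of about 12 events per cohort lost (5% risk, 5-30% found only in the record). The risk ratio need not be biased if under-reporting is equal across cohorts.

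The live-birth restriction is an unexplained choice for a maternal outcome, and it conditions on an event that exposure may affect. On the assumptions shown it loses under one case per cohort, and a true risk ratio of 2.0 would read about 1.9, well inside the sampling error of about 12 events. The bias has a direction but is probably small. The documents do not support a claim that the preeclampsia comparison is seriously distorted or would falsely reassure.

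**What to change.** 1. In Table 7-1, adopt the Section 7.7.2.4 definition: a maternal report confirmed in the medical record, or documentation in the record alone.
2. In Section 7.7.3.1.2, take preeclampsia/eclampsia out of the live-birth set. Analyse it in singleton pregnancies with known outcome that reached 20 weeks, stillbirths included, and keep the live-birth set as a sensitivity analysis.
3. Leave the live-birth restriction in place for small for gestational age and postnatal growth.

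The cost is wording in the protocol and matching text in the SAP. Outcome interviews for losses and releases for obstetric and hospital records are already planned (Sections 7.4.3.3 and 7.4.3.4), so no new data stream is needed.

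The downsides are modest. Records may be thinner and time at risk shorter for a few late losses. The 20-week entry point is borrowed from the protocol's split between spontaneous abortion and stillbirth and still selects on survival to that point, though less than live birth does.

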#### **7.7.3.2 Missing data**

Missing values typically occur in less than 5% of the cases for any single covariate. They are assumed to be missing at random. When there are missing values in any of the selected confounders, multiple imputation (MI) will be conducted, using the R package MICE (multivariate imputation by chained equations) (van Buuren and Groothuis-Oudshoorn, 2011). MI will be conducted for missing data using the entire dataset, i.e., on all cohorts combined.

For the outcome of SAB, for some cases the exact date of SAB might be unknown, and instead a window for possible SAB time is available. This is known as interval censored data, and can also be handled using MI (Pan, 2000). An exact SAB time will be imputed by sampling uniformly from the corresponding time window.

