### **7.4.3.2 Interim interview I and II (~20 and 32 weeks' gestation)**

Following the initial intake interview, participants will be sent a pregnancy exposure diary on which they will be asked to record any additional exposures (medications, vaccinations, vitamins, etc.) or events as the pregnancy progresses. Along with the pregnancy exposure diary, each woman will be sent a copy of the written informed consent document, and a research HIPAA compliant obstetric medical record release form.

Women who have enrolled in the study prior to 18 weeks post-LMP will be interviewed by telephone at 20-22 weeks post-LMP, 32-34 weeks post-LMP and within 0-6 weeks after the expected due date. Women who have enrolled between 18 and 20 weeks post-LMP will be interviewed at 32-34 weeks post-LMP and within 0-6 weeks after the expected due date.

Women who enrolled after 20 weeks post LMP and before 30 weeks post-LMP will be interviewed at 32-34 weeks post-LMP and within 0-6 weeks after the expected due date. Women who have enrolled after 30 weeks post-LMP will be interviewed within 0-6 weeks after the expected due date (See [Table 7-2](#)).

The purpose of these interviews will be to update records of pregnancy exposures and results of prenatal tests, to remind women to maintain the pregnancy exposure diary, to update phone number and address information, and to determine if the pregnancy has ended prior to the expected due date.

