Given the Phase III data supporting the siponimod approval for relapsing forms of MS was generated in the SPMS population, as reflected in the clinical studies section of the FDA approved labelling, it may transpire that siponimod is more likely to be prescribed to patients

who are older and with higher disability. Thus there is potential for channeling bias. To the extent that factors such as age and disability differ in exposed and comparison cohorts, these will be considered in adjusted analyses.

It is possible that women in the disease comparison group may have less severe disease than those who enroll in the siponimod exposed group. It is also possible that women in the siponimod exposed group will enroll earlier in pregnancy than either of the comparison groups. The study will monitor disease severity and gestational age at enrollment and discuss any modifications needed in recruitment strategies as the study progresses. Further, all three cohorts rely on volunteers and may not represent the entire population of exposed and unexposed women.

Although all possible efforts will be made to retain participants in the registry or follow up with their healthcare providers, some participants will be lost during follow up. It could be possible that participants lost during follow up and with missing data on outcomes may be different compared to those with complete follow up data. In previous OTIS studies, lost-to-follow-up rates have been low, typically <5%. However, the characteristics of women lost to follow up will be compared to those who are retained in order to understand the direction and magnitude of the bias due to loss to follow up.

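### Undated spontaneous abortions are imputed uniformly over their window although risk is highest early; with wide windows this lowers the Kaplan-Meier rate and can distort the crude hazard ratio

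*Protocol*

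**What the plan says.** Protocol section 7.7.3.2 (Missing data) notes that "for some cases the exact date of SAB might be unknown" and that only a window is then known. It treats this as interval censoring, to be handled by multiple imputation, and fixes the draw: "An exact SAB time will be imputed by sampling uniformly from the corresponding time window". It gives no condition or alternative.

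Four other places bear on this:
- Section 7.7.3.1.2: women are not followed from gestational age zero, so "survival analysis methods will be used to handle left truncation". A left-truncated Kaplan-Meier estimate at 20 weeks gives the rate in each cohort. A left-truncated Cox model gives the HR, and an adjusted HR follows by PS regression.
- Section 7.5.1: mean enrolment is at 7-10 weeks post-LMP. Registry enrolment typically begins after 7-8 weeks, "when the highest risk of spontaneous abortion has passed".
- Section 7.4.3.2: "Women who have enrolled in the study prior to 18 weeks post-LMP will be interviewed by telephone at 20-22 weeks post-LMP".
- Section 7.9: "It is also possible that women in the siponimod exposed group will enroll earlier in pregnancy than either of the comparison groups".

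**The concern.** A uniform draw is right only if losses are spread evenly over the window. If risk falls with gestation, the true date is more likely to lie near the start, and uniform draws are late on average. Repeating the draw in multiple imputation does not help, because every draw comes from the same wrong distribution.

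Both planned estimators depend on placing each loss in its correct gestational week. A loss moved later meets a larger risk set, because more women have enrolled by then, so it adds less to the cumulative hazard and the Kaplan-Meier rate falls. If one cohort enrols earlier, its early losses are carried into weeks where the other cohort has more women at risk. That undoes part of the gestational-age alignment that left truncation provides, and the crude HR moves away from 1 without any drug effect.

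SAB is a secondary outcome, but section 5 reports post-implantation loss in rats and embryo-fetal deaths and abortions in rabbits, so its rate will be read with care.

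**Working it through.** **Inputs from the Protocol.** Mean enrolment 7-10 weeks, SAB/stillbirth rate 10% and loss to follow-up 5% (section 7.5.1); 259 per group, relative risk 1.9, two-sided 0.05, Fisher's exact test (Table 7-4); left-truncated Kaplan-Meier and Cox (section 7.7.3.1.2).

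**Assumptions, because the Protocol gives no figure.** Share of losses undated: 10% to 100%. Window: 2 weeks, 4 weeks, or enrolment to week 20. Hazard: halving every 1.5, 2.5 or 4 weeks, with a flat hazard as control. Enrolment: mean 8.5 weeks (SD 2.5) in both cohorts, or 7.5 weeks (exposed) v 9.5 weeks.

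**1. The plan's own figure.** Exact enumeration of Fisher's test at 259 v 259 with 19% v 10% gives power 0.802, against the stated 80%. Table 7-4 stands. It says nothing about imputation.

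**2. How far a uniform draw is displaced.** With few losses overall, the event density is roughly proportional to the hazard. For a hazard falling at rate λ, the mean time after the start of a window of width W is 1/λ − W·e^(−λW)/(1 − e^(−λW)); a uniform draw has mean W/2. With halving every 2.5 weeks, λ = ln 2/2.5 = 0.277 and 1/λ = 3.607.
- W = 4: 3.607 − 4 × 0.330/0.670 = 1.64, against 2.00. Displacement about 0.36 week.
- W = 11.5 (enrolment at 8.5 to week 20): 3.607 − 11.5 × 0.0412/0.9588 = 3.11, against 5.75. Displacement about 2.64 weeks.

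Simulation gives the same order: about 0.1 week for 2-week windows, 0.2-0.4 for 4-week windows and 2.2-4.6 for enrolment to week 20.

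**3. SAB rate.** Large-sample simulation with no drug effect. The hazard is set so that 10% of women enrolled at mean 8.5 weeks have an SAB before week 20, and Kaplan-Meier is taken from week 6. Halving every 2.5 weeks, window from enrolment to week 20:
- Equal enrolment: 0.163 with true dates; 0.159, 0.151 and 0.143 at 10%, 30% and 50% undated. At 30% the relative fall is (0.163 − 0.151)/0.163 = 7%.
- Enrolment 7.5 v 9.5 weeks, 30% undated: later-enrolling cohort 0.164 to 0.148 (10% relative); earlier-enrolling cohort 0.164 to 0.158 (4%).
- Across the assumed slopes, the fall at 30% undated is roughly 2 to 16% in relative terms.
- Windows of 2-4 weeks and at most 50% undated, equal enrolment: fall of 0.003 or less. In an earlier-enrolling cohort the rate is about unchanged.

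**4. Crude HR under no effect.** Exposed 7.5 v comparator 9.5 weeks, halving every 2.5 weeks unless stated:

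| Window | 10% undated | 30% | 50% | 100% |
|---|---|---|---|---|
| Enrolment to week 20 | 1.03 | 1.11 | 1.20 | 1.42 |
| Same, halving every 1.5 weeks | 1.08 | 1.24 | 1.41 | 1.88 |

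With 4-week windows and halving every 2.5 weeks, the HR is 1.00-1.02 at up to 50% undated and 1.05 at 100%. Across the slopes, 30% undated with windows from enrolment to week 20 gives about 1.05 to 1.24. With equal enrolment or a flat hazard there is no HR bias. With enrolment reversed (exposed 9.5 v 7.5), the HR at 30% undated is 0.895.

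**5. Against sampling error.** At 259 per group and 10%, 2 × 259 × 0.10 = 51.8 losses, so the standard error of the log HR is about 2/√51.8 = 0.278. An HR of 1.116 (the 30% case before rounding) is ln 1.116/0.278 = 0.110/0.278, about 0.4 standard errors. False-positive rates at a nominal 5%, halving every 2.5 weeks: 4.5% with true dates; 4.8% (30% undated, 4-week window); with enrolment to week 20, 5.7% at 30%, 8.3% at 50% and 21.5% at 100%.

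**6. PS adjustment on enrolment week.** Window from enrolment to week 20, smaller runs with a standard error of log HR of about 0.03: crude 1.12, 1.14 and 1.47 at 30%, 50% and 100% undated become 1.01, 0.95 and 1.03 with a linear PS, or 1.07, 1.02 and 1.17 with a richer PS.

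**7. Conditional draws.** At 30% undated, window from enrolment to week 20, exposed enrolling earlier: HR 0.998 (true dates 0.998, uniform 1.116); comparator rate 0.164 (true 0.164, uniform 0.148).

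**The case against.** The strongest reply is that the wide-window case takes the contact schedule for the uncertainty about the date. The outcome interview asks when the loss occurred (section 7.4.3.3), and releases are sought for pathology and prenatal-diagnosis records (section 7.4.3.4). Undated losses may be few and their windows short. This stands. Nothing in the Protocol says that a window runs from enrolment to week 20, and with windows of about 4 weeks the effect is negligible. At 10% losses in 289 women, 30% undated is only about nine per cohort (289 × 0.10 × 0.30 = 8.7).

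The second reply is that safeguards exist. Gestational age at enrolment is a listed confounder (Table 7-1), all potential confounders enter the PS (section 7.7.3.1.1), and the adjusted SAB HR uses that PS. A sensitivity analysis by gestational age at enrolment is planned, and enrolment timing is monitored (section 7.9). This stands for the adjusted HR, where most of the bias goes. It does not help the Kaplan-Meier rate or the crude HR, and the sensitivity analysis would use the same imputed dates.

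Three stronger readings are tempting but not supported:
- **That risk falls steeply.** Section 7.5.1 supports a fall but gives no slope.
- **That the rate drops in every cohort, or that the HR is always inflated.** With narrow windows the earlier-enrolling cohort's rate is about unchanged. The direction of the HR bias depends on who enrols earlier.
- **That draws may fall before enrolment.** Only currently pregnant women are eligible and enrolment after the pregnancy has ended is excluded (section 7.2.2), so no possible SAB date precedes entry. Coding that bound is ordinary SAP detail.

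**Conclusion.** The uniform rule conflicts with the Protocol's own statement about when SAB risk is highest, and it tends to place undated losses too late. The consequences are conditional. The Kaplan-Meier rate is lowered when windows are wide, mainly in later-enrolling cohorts. The crude HR moves above 1 if exposed women enrol earlier, below 1 if they enrol later, and not at all with equal enrolment.

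The size rests on three quantities absent from the Protocol (undated share, window width, hazard slope) and, for the HR, on an assumed two-week difference in enrolment. With 30% undated and windows from enrolment to week 20, the crude null HR is about 1.05 to 1.24 and the rate falls by roughly 2 to 16% in relative terms. With windows of about 4 weeks, or few undated losses, the HR is at most about 1.03. A reader should not infer that the adjusted SAB comparison is seriously biased, or that the primary outcome is touched. This is a minor point, worth correcting because the remedy is cheap and restores the true values in simulation.

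**What to change.** Replace the last sentence of section 7.7.3.2. Within multiple imputation, draw each undated SAB time from the estimated gestational-age distribution of SAB (left-truncated estimator, cohorts pooled), conditional on the woman's window and limited to the time between enrolment and 20.0 weeks. Alternatively, fit a left-truncated, interval-censored Cox model directly.

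Report the number of undated losses and the window widths by cohort, so that readers can judge whether the issue is material. Add two sensitivity bounds, with every undated loss set to the earliest and then to the latest date in its window.

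The cost is one changed sentence and a little more programming. No new data are needed.
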